5.5 N/A

5.6 N/A

5.7 There will be post intervention (2.5-3 months after baseline measurements) and 5-month follow-up assessment as described in Table 4 below.

Table 4. Efficacy Outcomes		
Outcomes	Measures / Expected Outcomes	Time
Dietary intake	3-day food records (ASA24™) / Food intakes (e.g., fruit and vegetables ↑), daily food variety ↑, diet quality (e.g., HEI fruit ↑, vegetables ↑, plant protein ↑)	T1, 2,3
Mealtimes behaviors	Brief Autism Mealtimes Behavior Inventory  via REDCap / Problematic behaviors ↓.	T1,2,3
Weight status (height and weight)	A stadiometer/ruler and a scale; birth to 36 months, weight-for-length%tile based on the CDC growth chart.  BMI for parents	T1 & 3
Feeding behaviors	Child Feeding Questionnaire via REDCap	T1 & 3
Demographics	A survey through the REDCap.	T1
Health conditions	Family history of ASD and comorbid health conditions such as epilepsy, sleep disorders, and anxiety disorders through the REDCap.	T1 & 3

\*T1: baseline; T2: post intervention; T3: 5-month follow-up

## 6.0 Data and Specimen Storage for Future Research

6.1 Data will be collected and maintained in accordance with legal and ethical standards and will be centrally stored in a master database. RedCap is a secure web application for research studies in HIPAA compliant environments, which will be used to collect data, except the dietary intake data that will be collected through the ASA24 online system. RedCap will allow for data to be entered and uploaded to a central, secure database, while prohibiting access outside USF. Providers and parents will be emailed a link to the RedCap-based surveys.

Only principal investigator and study staff members will have access to files containing identifiers such as contact information of study participants (providers and parent-child dyads). These files will be stored in an encrypted form in a password protected secure database. These files will be used only for data collection. The collected data will be deidentified. Participants' information that individuals can be identified with will be removed from the study data files. The deidentified data will be stored as study data files in a password protected USF computer in a locked USF office.

For data security and confidentiality of study data files, we will develop data management and security policy that all users of the study data should adhere to. Only authorized users can have access to and possess the data files to conduct data analyses. Authorized users include principal investigator, study data managers, study data analysts. Other internal users and external users should be given authorization by the principal investigator. All users must sign a data security agreement and send a copy of the agreement to the principal investigator. Users should not share a copy of study data files. All users must adhere to the data security and confidentiality procedures. All users other than principal investigator and study data managers must destroy study data files upon the completion of a study as specified in the agreement.

6.2 The final dataset will include self-reported demographic, dietary, and behavioral data from 3-day food records, a validated mealtime behavior questionnaire, and a survey.

Obesity exploratory outcome data will be collected with children's and parents' height and weight. All datasets will be de-identified with numeric numbers.

6.3 We will make the data and associated documentation available to users under a data-sharing agreement that provides for: (1) a commitment to using the data only for research purposes such as a review of similar intervention studies and not to identify any individual participant; (2) a commitment to securing the data using appropriate computer technology; and (3) a commitment to destroying or returning the data after analyses are completed. Our aggregated data and results will be available through ClinicalTrial.gov following their requirement and guidelines.

## **7.0 Sharing of Results with Subjects**

7.1 Because the proposed study is a preliminary efficacy study (Stage 1 clinical trial), without clear understanding of the intervention content and context, the data can be misinterpreted. Thus, results will not be shared with anyone outside the research team or without a data-sharing agreement.

## **8.0 Study Timelines**

8.1 Activities for Aim 1 will start in October 2021 and Aim 2 is planned to be started in January 2022. The project will end in July 2023. Participants will be recruited in a rolling basis. For Aim 2 (RCT), each parent-child dyad will have three data collections: baseline (T1), post-intervention (T2), and 5-months follow-up from baseline (T3). The Enhanced Usual Care (EUC) comparison group will receive one intervention session and periodic written materials from We Can!.

## **9.0 Inclusion and Exclusion Criteria**

### **9.1**

#### **Level 1 – Early Intervention (EI) service providers:**

Inclusion criteria: Full-time employees of EI services who have children with ASD in their service at the time of recruitment are eligible to participate.

#### **Level 2 – Parent-child dyads:**

Inclusion criteria:

- Children should be enrolled in the EI service. Children who are determined as “at risk/monitored for ASD” at the time of screening or diagnosed with ASD determined by clinical assessment such as the Autism Diagnostic Observation Schedule (ADOS) or another validated evaluation tool such as Gilliam Autism Rating Scale (GARS-3). Children birth to 36 months are eligible for the EI

services, and therefore, age of our research participants will range from birth to 36 months.

- Parents should be 18 years or older and speak fluent English and/or Spanish

9.2

Level 1 – Early Intervention (EI) service providers:

Exclusion criteria: Non-EI service providers and who do not work with children with ASD.

Level 2 – Parent-child dyads:

Exclusion criteria:

- Children who are on exclusive breastfeeding, medicines that may interact with appetite and food consumption, having severe GI conditions such as irritable bowel syndrome, diagnosed with feeding disorders or severe food selectivity, or other serious medical comorbidities such as cancer.
- Parent and child with ASD who have previously participated in a similar nutrition intervention study will also be excluded.
- Parent's first language is not English or Spanish.

9.3 If participants are diagnosed with other serious illnesses or medication condition other than ASD, they will be excluded from the study. The intervention and EUC program will be implemented within the EI service schedules. EI providers and parent-child dyads work closely together within their regular EI programs regardless their participation status in our study. If either an EI provider or parent-dyad wish to withdraw from the study, it is likely that they will discuss and made a decision together.

9.4 The study will include employees from the USF Florida EI program, Early Steps, since the USF Early Steps EI providers will be recruited.

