### **3.0 Background**

3.1 The prevalence of ASD has increased drastically in recent years, with current estimates at 1 in every 54 (more than 2 million) children affected in the United States, which is approximately 10% higher than the estimate in 2014 and 175% or 2.8 times higher than the first estimates reported in 2000. In addition, Florida has the highest prevalence of ASD (4.88% compared to 2.9%, the national average). Without intervention, individuals with ASD are at significant risk for developing diabetes, coronary heart disease, and cancer by midlife.

Unhealthy food choices in children with ASD are a growing concern with potential for lifelong impact. Children with ASD tend to consume few fruits and vegetables and excess calories from high-energy dense foods, including starches, sugar-sweetened beverages, and other highly processed foods and snacks, contributing to increased rates of obesity and other diet-related diseases. ASD-specific problematic mealtime behaviors and food selectivity should be addressed. Prior research reported that children with ASD experience up to 5 times more feeding problems, including problematic mealtime behaviors (e.g., not staying seated and showing aggressive behaviors or tantrums during mealtime) and food selectivity (i.e., only eating a narrow variety of foods), compared to their neurotypical peers, which may increase the risk for developing poor eating behaviors and inadequate nutrient intakes. Lower intakes of protein, calcium, phosphorus, riboflavin, and vitamin B12 have been reported in children with ASD. Due to these feeding problems, parents' attempts to expand their children's diets may be more challenging. Therefore, interventions for this population should address ASD-specific feeding challenges.

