Training session materials include a 90-minute presentation prior to the intervention implementation and a 90-minute mid-training session in-between lesson 4 and 8. Both training sessions have been developed and pilot-tested in our preliminary feasibility study, and all enrolled EI providers participated in those sessions without attrition. On-going EI provider support will be provided by offering co-coaching the sessions when the EI providers need assistance on nutrition-specific activities. Randomly selected sessions (20%) will be observed and check whether all lesson components are consistently implemented as designed across EI providers, adapting the 5-point scale from a previous clinical trial. We will examine whether our intervention sessions fit the context of the EI services as well as the needs, expectations, and values of the EI providers, using an exit survey. Using those selected sessions, compatibility of the intervention content and activities for different levels of children's autism features and symptoms will also be examined from the observation or video-recorded sessions. EI providers and parents will be invited for a semi-structured interview at 5-month follow-up. The interviews will be audio/video recorded for transcriptions.

Three-day food record is a gold-standard assessment for dietary intake of individuals. Three 24-hour food records will be completed by parents using the NCI's Automated Self-administered 24-Hour Dietary Recall. Research assistants (RA) will provide guidance as needed. We focus on average daily dietary intakes by food groups (i.e., fruit, vegetables, grain, protein, and dairy) and daily food variety. For all children aged 2 years or older, diet quality will be determined by the Healthy Eating Index's total and sub-component scores (adequacy vs. moderation food categories). The Brief Autism Mealtime Behavior Inventory (BAMBI) will be used to assess children's mealtime behaviors. The BAMBI is a validated assessment tool that contains 18 questions and uses a 5-point Likert scale. A trained RA (single-blinded) will assess children's height and weight with a professional stadiometer and a weight scale following the standardized protocol used in previous studies. As a standard weight status assessment for birth to 36 months, weight-for-length based on the CDC growth chart will be calculated. Parent BMI will be calculated and used as a covariate in data analysis. If height and weight

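### Infants fed only formula, or breast milk plus formula, can be randomised, so starting solid food adds developmental change and variance to the intake, variety and mealtime outcomes

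*Protocol*

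**What the plan says.** Protocol 9.1 sets no lower age limit: "age of our research participants will range from birth to 36 months". A diagnosis is not required, because the same section also admits "Children who are determined as “at risk/monitored for ASD” at the time of screening". In 9.2 the only exclusion by feeding mode is the opening item of "Children who are on exclusive breastfeeding, medicines that may interact with appetite and food consumption". The other child exclusions concern medicines, gastrointestinal conditions, feeding disorders or severe selectivity, serious comorbidity and earlier participation in a similar study. Neither document mentions formula or requires that the child eats solid food at baseline.

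On outcomes, Protocol 5.2 states "We focus on average daily dietary intakes by food groups (i.e., fruit, vegetables, grain, protein, and dairy) and daily food variety" and "The Brief Autism Mealtime Behavior Inventory (BAMBI) will be used to assess children's mealtime behaviors". Neither has an age limit, and Table 4 schedules both at T1, T2 and T3. Diet quality is treated differently: "For all children aged 2 years or older, diet quality will be determined by the Healthy Eating Index". On timing, Protocol 5.7 states "There will be post intervention (2.5-3 months after baseline measurements) and 5-month follow-up assessment".

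Protocol 16.1 and the SAP (Aim 2b) plan variance and effect sizes from pre to post and from post to follow-up, and a nonparametric longitudinal comparison of change between arms. Allocation is by random number generator (Protocol 5.1), with no stratification stated. The SAP's list of potential confounders names parent age but neither child age nor feeding stage. Age otherwise enters only through a correlation of demographic variables with the outcomes of Autism Eats.

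**The concern.** A healthy infant fed only formula, or breast milk plus formula, meets every stated criterion. At T1 that child has no fruit, vegetable, grain or protein-food intake and little or no food variety. Dairy may differ, depending on how formula is coded. Problem behaviours of the kind given in Protocol 3.1, such as "not staying seated and showing aggressive behaviors or tantrums during mealtime", are hard to interpret in a child who does not yet take meals.

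If the child starts complementary foods before T2 or T3, intake and variety rise whichever arm the child is in. That rise is in the direction Table 4 lists as the expected benefit. It enters the pre-post effect sizes and the variance of change, which are the quantities this pilot is meant to report. Diet quality is not affected in this way, because it has its own age limit.

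**Working it through.** **Does anything in the documents close the gap?** Three places could.

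- Eligibility (Protocol 9.1 and 9.2): no minimum age, no solid-food requirement, no mention of formula.
- Outcome definitions (Protocol 5.2 and Table 4): an age limit for the Healthy Eating Index only.
- Allocation and analysis (Protocol 5.1 and 16.1; SAP Aim 2b and the confounder list): no stratification stated, and no adjustment for child age or feeding stage.

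None of them does.

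**How large could the effect be?** The plan has no figure to reproduce; the SAP says a sample size calculation is not required. The inputs are:

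- Arm size n: 24 (Protocol 5.1), or 15 if the SAP's N=30 is read as 30 dyads split 1:1.
- Milk-only infants k in one arm: not given; assumed 1, then 2.
- Extra change D from weaning, in units of the SD of change among the other children: not given; assumed 1 to 8/3 (about 2.7). The top of the range corresponds to 8 more foods a day against an SD of 3, both assumptions.

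With p = k/n:

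- shift in the arm's mean change = p × D
- SD of change relative to the other children = √(1 + p(1 − p)D²)

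For k = 1, n = 24, p(1 − p) = (1/24)(23/24) = 0.0399:

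- D = 1: shift 1/24 = 0.04 SD; SD = √1.0399 = 1.020, up 2%.
- D = 8/3: shift 2.667/24 = 0.11 SD; SD = √(1 + 0.0399 × 7.111) = √1.284 = 1.133, up 13%.

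| n per arm | k in that arm | p(1 − p) | Mean shift (SD) | Rise in SD of change |
|---|---|---|---|---|
| 24 | 1 | 0.0399 | 0.04 to 0.11 | 2% to 13% |
| 24 | 2 | 0.0764 | 0.08 to 0.22 | 4% to 24% |
| 15 | 1 | 0.0622 | 0.07 to 0.18 | 3% to 20% |
| 15 | 2 | 0.1156 | 0.13 to 0.36 | 6% to 35% |

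The plan does not say how effect sizes will be standardised. If the inflated SD is the divisor, part of the shift cancels. For example, with no change in the other children, 0.111/1.133 = 0.098 instead of 0.111.

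**How likely is imbalance?** If two such infants enter and the arms are of equal size, the chance that both fall in the same arm is 23/47 = 49% at N=48 and 14/29 = 48% at N=30.

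**Is the between-arm contrast biased?** Allocation is random, so each arm expects the same number of these infants, and those in the control arm also start solids. The expected contribution to the difference in change is therefore zero. A particular trial can still be shifted by chance.

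**The case against.** The strongest reply is that the randomised control arm handles weaning, since Aim 2b compares change between arms. This stands. A reader might infer that weaning biases the treatment comparison, but the documents do not support that; the harm is limited to within-arm change, variance and chance imbalance. The planned rank-based tests also limit the leverage of one extreme child on the tests, though not on reported means, SDs and intervals based on them.

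Three other inferences go too far. That every baseline outcome is zero is not shown: dairy is one of the food groups, and the items of the mealtime inventory are not in the documents, so neither its floor nor the direction of its change can be stated. That the reason for excluding breastfed infants applies equally to formula-fed infants cannot be shown, because no reason is given. That feeding questions already asked at screening would identify these children is not supported either: the pre-consent check in Protocol 16.5 is described for ASD or at-risk status only, and the Child Feeding Questionnaire is a T1 and T3 measure.

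It is also fair to say that infants seem to be intended participants. Lesson 1 covers feeding milestones for infants and toddlers, and Lesson 3 covers new foods. That supports keeping a young age range, but it does not make food-group and variety changes interpretable for a child who eats no food at T1. Finally, this is a pilot with feasibility benchmarks, and the SAP itself says outcome evaluation suits a fully powered trial better. That limits the consequence, but the variances and effect sizes are still what the pilot will report.

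**Conclusion.** The eligibility gap is real and nothing elsewhere in the documents closes it. Its effect is modest. With one milk-only infant in an arm of 24 and an extra weaning change of 1 to 2.7 SD, that arm's mean change moves by 0.04 to 0.11 SD and its SD of change rises by about 2% to 13%. The effect grows with the number of such infants and is larger at 15 per arm. These sizes rest on assumed values for the number of infants and the weaning change; the true number may be zero. Expected between-arm bias is zero. The change is worth making because it is cheap and protects the estimates the pilot is meant to supply.

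**What to change.** In Protocol 9.2, replace *on exclusive breastfeeding* with *not yet eating complementary foods (fed only breast milk and/or formula)*. Check it with one added screening question, or from the T1 food records; both documents place randomisation after baseline data collection, so those records are available before allocation. If any such child is already enrolled, report the food-group, variety and mealtime-inventory outcomes with and without children not eating complementary foods at T1.

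The cost is one screening question and the loss of a few milk-only infants, which slightly narrows the population. Infants who have only just started solids would still enter, so the criterion reduces the developmental change but does not remove it.

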## **10.0 Vulnerable Populations**

10.1 Children from birth to 36 months diagnosed with ASD. All efforts will be made to safeguard the children with ASD. Children's privacy and confidentiality will be protected, as will their rights, safety, and well-being. The intervention materials have been written to address mealtime and eating behaviors in children with ASD and a pilot study was conducted in this population. As mentioned, the possible risks of the study are minimal. The direct and potential benefits outweigh the risks of the intervention.

Resources and specialists will be made available to parent-child dyads who experience any adverse reactions, e.g., discomfort answered questions about dietary behaviors or being weighed by the research staff.

## **11.0 Local Number of Subjects**

11.1

For Aim 1, 10 EI providers and 10 parents will be enrolled.

For Aim 2, 30 EI providers and 48 parent-child dyads (48 parents and 48 children) will be enrolled.

## 12.0 Recruitment Methods

### 12.1

 Email	 Online/Social Media Advertisement
 Flyer	 Record Review
 Letter	 SONA
 News Advertisement	 Other

### 12.2

For aim 1, the EI providers and parents will be recruited through the county EI services. The research team members will send out emails to the EI directors and ask them to distribute the flyers to EI providers. The EI service directors/administrators/providers will distribute the parent flyer to potentially eligible parents. Anyone who is interested in participating in the study will be asked to contact the research team.

For aim 2, EI providers and parent-child dyads will be recruited through email and flyer as described below.

Early Intervention (EI) service providers: Providers will be first recruited through the EI program that covers Hillsborough and Polk Counties in Florida. There are approximately 180 EI providers in these two counties. The director of the EI services in these counties is a Co-I of this study. A recruitment flyer emphasizing the importance of early nutrition intervention and common mealtime behavioral problems among children with or at risk/monitored for ASD will be distributed by email and through appropriate social media platforms (e.g., Facebook). Trained research staff and/or the PI will conduct a brief introductory session at one of the regular provider meetings to introduce the study and use a sign-up sheet to recruit potential providers who are willing to participate in the study. Recruitment materials will be distributed repeatedly until the target participant number is met.

Parent-child dyads: EI providers who agree to participate will inform potentially eligible parents about the study and recruit them to contact the research team for study participation. A parent recruitment flyer will be distributed through the EI services and/or directly by the EI providers to eligible parents.

12.3 For vulnerable population described in section 10, at the intake and then subsequently at the time of each follow-up assessment, participants are reminded that they may discontinue any procedure at any time, or withdraw from the study altogether, without

prejudice, and afforded opportunities to ask questions about any facet of the study. We take great care to assure that neither participants nor their families feel any coercion to take part in the project, and that participation in the study is a positive and affirming experience for those who do take part. Study participants are assured that they are free to withdraw at any time without prejudice and will still receive the same quality of services.

## **13.0 Withdrawal of Subjects**

13.1 Withdrawals without participants' consent are not anticipated.

13.2 We will contact participants who withdraw by email to ask the reason for withdrawal and conduct an interview if possible. To manage dropout, we will first assess whether dropout was related to certain baseline measures and demographic variables. We will report dropout rate and compare distributions of baseline measures and demographic variables.

## **14.0 Risks to Subjects**

14.1 Potential risks are minimal. Participants may experience psychological discomfort during intervention sessions or while answering survey questions or having their height and weight measured. All survey measures are online, and a virtual session will be available for participants' height and weight measurement, considering the risks associated with COVID-19. For program implementation, EI providers will adhere to their organizational recommendations and procedures for COVID-19 safety measures. Our program can be implemented in person or through telehealth with the manual that include detailed instructions for both modalities. Therefore, participants won't have an increased risk for getting COVID-19 based on their status of study participation. Participants will still be informed that, there is a risk of transmission of the novel coronavirus if they participate in any research activities in person, and that while precautions will be taken, we cannot guarantee that the participant will not be exposed to the virus.

